4.5 Withdrawal of individual subjects

A subject will be withdrawn if ANY of the following criteria are met:

- The subject wishes to withdraw from further participation
- The subject is significantly noncompliant with the Protocol
- The subject becomes pregnant
- Continuing in the study would be detrimental to the subject's safety in the opinion of the Investigator, e.g.,
 - The subject experiences intolerable AEs or SAEs
 - The subject has clinically significant changes in safety parameters at any of the post-dose time points, as confirmed with a repeat assessment performed as soon as possible after the initial out-of-range result

In addition, a subject may be withdrawn at any time for reason(s) other than those listed here.

If a subject is discontinued prematurely from the study, the date the subject is withdrawn from the study and the reason for withdrawal will be recorded on the electronic case report form (eCRF).

In case of withdrawal of a subject, the Follow-up assessments should be performed, as far as possible (Section 5.2.3).

Any withdrawal due to an AE or for any safety reason should be assessed for seriousness according to Section 8.2.

Any unresolved AE or SAE will be followed up according to Section 8.9.

In the event that a subject elects not to return to the clinic for the end of study visit, the Investigator must make every effort to contact the subject to review all AEs. In the event that a subject drops out of the study at any time, the reason for discontinuation must be fully documented in the source documents and the eCRF. The study centre personnel will document the AEs and any other assessments in the source documents and will make every effort to complete all required end of study assessments.

Subjects withdrawn for non-treatment-related reasons may be replaced at the discretion of the Sponsor and Investigator. Replacement subjects will receive the treatments intended for the withdrawn subject.

4.6 Study stopping criteria

If any subject experiences either a severe AE which the Investigator considers is related to MCI-186, or a severe or serious adverse drug reaction, then the subject is to be immediately withdrawn and no further subjects will be recruited. The withdrawn subject should be followed up as detailed in Section 4.5.

4.7 Lifestyle restrictions

Subjects will be advised that they must adhere to the following restrictions:

4.7.1 Attendance

- Subjects must be available to attend visits according to the Protocol.
- Subjects must be available for overnight stays in the study centre from Day -1 to Day 3.

4.7.2 Alcohol restrictions

- Subjects should refrain from consuming food or drink containing alcohol in the 48 hours before each visit and whilst confined to the study centre.
- Subjects should avoid excessive consumption (>2 units per day) of food or drink containing alcohol at all other times from the Screening Visit until the Follow-up assessment.

4.7.3 Xanthines

Subjects should refrain from consuming food or drink containing caffeine and methylxanthine (e.g., coffee, tea, cola, energy drinks or chocolates) in the study centre from Day -1 to Day 3.

4.7.4 Smoking

No smoking or using tobacco- or nicotine-containing products (snuff, chewing tobacco, cigarettes, cigars, pipes, e-cigarettes or nicotine replacement products) will be allowed in the study centre from at least 4 hours before dosing to 6 hours after dosing, and from at least 1 hour before scheduled ECG and vital signs examinations until the end of each examination.

4.7.5 Contraception

Female subjects of child-bearing potential* must be willing and able to practice birth control for the duration of the study, from the Screening Visit or at least 2 weeks before IMP administration until 30 days after IMP dosing. Male subjects must be willing and able to practice birth control from the time of IMP dosing until 90 days after IMP dosing.

- **Female subjects** must be willing to use a highly effective method of birth control (i.e., contraceptive measure with a failure rate of <1% per year), in conjunction with male barrier contraception (i.e., male condom with spermicide). Highly effective methods of contraception include:

- Placement of an intrauterine device or intrauterine system.
- Established use of oral, injected or implanted hormonal methods of contraception associated with inhibition of ovulation.
- Male sterilisation (with the appropriate post-vasectomy documentation of the absence of sperm in the ejaculate). (For female subjects on the study, the vasectomised male partner should be the sole partner for that subject.)
- Bilateral tubal ligation.
- True abstinence: when this is in line with the preferred and usual lifestyle of the subject. (Periodic abstinence [e.g., calendar, ovulation, symptothermal, post-ovulation methods] and withdrawal are not acceptable methods of contraception.)

Female subjects must not donate ova for the duration of the study, from the time of the first dose of IMP until 3 months after the last dose of IMP.

- **Male subjects** with partners of child-bearing potential must use a barrier method of contraception (i.e., male condom with spermicide) in addition to a second method of acceptable contraception used by their female partners. In addition to the list of highly effective contraception methods above, other acceptable methods of contraception include:

- Progesterone-only oral contraception, where inhibition of ovulation is not the primary mode of action.

- Cap, diaphragm or sponge with spermicide.

Male subjects must not donate sperm for the duration of the study, from the time of IMP dosing until 90 days after IMP dosing.

*Note: Women are considered to be of child-bearing potential unless they meet one of the following criteria as documented by the Investigator:

- Postmenopausal for at least 1 year, confirmed by FSH assessment (>40 mIU/mL).
- Hysterectomy, bilateral oophorectomy or salpingectomy.
- Congenital sterility.

Subjects must not have unprotected sexual intercourse during the study.

4.7.6 Diet

- While confined to the study centre, subjects will receive standardised meals at scheduled times.
- Subjects should have breakfast on Day 1 after the pre-dose assessment including PK blood sampling and at least 30 minutes prior to the start of IMP administration.
- Lunch on Day 1 (dosing day) will be provided at approximately 13:00 (i.e., after PK blood collection of 3 hours post-dose).
- Subjects will be required to fast (except for water) at least 5 hours prior to routine safety blood sampling.
- Subjects should refrain from ingesting food or drink containing poppy seeds in the 72 hours before Screening and from 72 hours before the check-in on Day -1.

4.7.7 Physical activity restrictions

- Must not participate in heavy physical training or excessive exercise (e.g., long distance running, weight lifting), or any physical activity to which the subject is not accustomed from 7 days before IMP dosing, during the study and until the Follow-up assessment.

4.7.8 Blood donation

- Subjects must not have donated one or more units of blood (450 mL) in the 3 months prior to Screening, or plasma in the 7 days prior to Screening, or platelets in the 6 weeks prior to Screening.
- Subjects must agree not to donate blood for 3 months after the last Follow-up assessment.

5 STUDY PLAN

Study assessments are summarised in the time and events schedule (Table 5).

Table 5 Time and events schedule

Study Period	Study Day	Screening			Treatment Hospitalisation			Follow-up		
		-21 to -2	-1	1	2	3	7 (+2)			
Time Point										
Informed consent	X									
Confinement										
Outpatient	X	◀								
Inclusion/exclusion criteria	X	X	X							
Demography & medical history	X									
Physical examination	X	X	X ²							
Weight	X	X								
Height	X									
BMI	X	X								
Vital signs	X	X	X							
12-lead ECG	X	X	X							
Urine drugs of abuse & breath alcohol test	X	X								
Biochemistry, haematology, coagulation & urinalysis	X	X						X	X	X
C-SSRS	X							X		
Hepatic impairment assessment (Child-Pugh classification; Group 1 only)	X	X								
eGFR	X	X						X	X	X
Hepatitis B & C and HIV	X									
Pregnancy test in females	X	X								
Protein binding blood sampling	X									
IMP administration					◀					
PK sampling (blood) ³					■	■	■	■	■	■

Abbreviations: AE=adverse event; BMI=body mass index; C-SSRRS=Columbia-Suicide Severity Rating Scale; ECG=electrocardiogram; eGFR=estimated glomerular

filtration rate; HIV=human immunodeficiency virus; IMP=Investigational Medicinal Product; PK=pharmacokinetic.

1. IMP administration starting time. IMP will be administered over 60 minutes. The permitted infusion time window is ± 3 minutes
2. Abbreviated physical examination only
3. The time windows for PK sampling during the study are as follows. All times relate to the infusion start time:

- pre-dose: -60 to -30 minutes  ± 5 minutes
-  ± 3 minutes from end of infusion
-  ± 5 minutes
-  ± 15 minutes

5.1 Subject informed consent

Prior to performing any study procedures, the Investigator (or designated personnel) will ensure that the subject is given full and adequate oral and written information about the study and the subject must sign the ICF, as described in Section 11.2.1.

5.2 Description of study phases

5.2.1 Screening

Screening assessments will be performed from Day -21 to Day -2. There may be more than one Screening Visit.

Subjects will be requested to attend the study centre after a 5-hour fasting period (apart from water). Written informed consent will be obtained before any screening procedures are performed. The following assessments will be performed (refer to Table 5 for further details):

- Written informed consent
- Verify inclusion/exclusion criteria
- Medical history
- Demography
- Physical examination (including height, weight and BMI)
- 12-lead ECG
- Vital signs (including standing and supine blood pressure, pulse rate and body temperature)
- Routine laboratory evaluations (biochemistry; haematology; coagulation; urinalysis; serology [HBsAg, HCVAb, HIV antigen/antibodies]; screening for drugs of abuse and alcohol; pregnancy test and FSH for females only)
- Degree of hepatic impairment by Child-Pugh classification (Group 1 only)
- eGFR assessment using the MDRD formula
- AE and concomitant medication recording

Re-screening will be allowed once if the subjects agree to perform re-screening in the ICF, with the exception of subjects who have received the IMP. A new written informed consent will not be necessary. Re-screening will be performed within 3 months after first Screening. If re-screening occurs within 20 days of the first Screening assessment and before Day -1 (admission to the study centre), only deviant parameters will be re-measured. Results of the Screening assessment will be replaced with the latest assessment.

5.2.2 Treatment hospitalisation period (Day -1 to Day 3)

Subjects who successfully complete pre-admission Screening will return to the study centre on the morning of Day -1 and will remain on-site until Day 3. Inclusion and exclusion criteria will be reviewed to confirm eligibility on admission (Day -1) and at Day 1 pre-dose. Eligible subjects will proceed to dosing.

Any subject who does not receive a single dose of IMP will be considered a screen failure (this includes subjects who successfully complete the pre-admission Screening, but fail on study eligibility criteria at admission or Day 1 pre-dose).

5.2.2.1 Baseline phase (Day -1 to Day 1 [pre-dose])

The following procedures will be performed on Day -1 (refer to Table 5 for further details):

- Verify inclusion/exclusion criteria
- Physical examination (including weight and BMI)
- 12-lead ECG
- Vital signs (including supine blood pressure, pulse rate and body temperature)
- Routine laboratory evaluations (biochemistry; haematology; coagulation; urinalysis; screening for drugs of abuse and alcohol; pregnancy test for females only)
- C-SSRS (see Appendix 1 in Section 14)
- Degree of hepatic impairment by Child-Pugh classification (Group 1 only)
- eGFR assessment using the MDRD formula
- Blood sampling for protein binding
- AE and concomitant medication recording

Re-assessment of Day -1 will be allowed once if the subjects agreed to perform re-assessment in the ICF, except for subjects who have been re-screened or have received the IMP. A new written informed consent will not be necessary. Re-assessment will be performed within 20 days between Screening and rescheduled Day -1. Only deviant parameters will be re-measured. Results of the Day -1 assessment will be replaced with the latest assessment.

The following procedures will be performed at pre-dose on Day 1 (refer to Table 5 for further details):

- Verify inclusion/exclusion criteria
- Abbreviated physical examination
- 12-lead ECG
- Vital signs (including supine blood pressure, pulse rate and body temperature)
- Blood sampling for PK analysis
- AE and concomitant medication recording

5.2.2.2 Treatment phase (Day 1 to Day 3)

Only subjects meeting all the inclusion and exclusion criteria and who are suitable for the study, will be included into the treatment phase.

A single IV infusion of 30 mg MCI-186 will be administered over 60 minutes on the morning of Day 1. The permitted infusion time window is ± 3 minutes.

The following assessments will be performed during the treatment phase (refer to Table 5 for further details):

- Abbreviated physical examination (including weight on Day 2) and physical examination (including weight on Day 3)
- 12-lead ECG
- Vital signs (including supine blood pressure, pulse rate and body temperature)
- Routine laboratory evaluations (biochemistry; haematology; coagulation; urinalysis)
- C-SSRS (Day 2 only; see Appendix 1 in Section 14)
- eGFR assessment using the MDRD formula

- Blood sampling for PK analysis [REDACTED] [REDACTED] all times relate to the infusion start time)
- AE and concomitant medication recording

5.2.3 Follow-up (Day 7 +2 days)

Subjects will return to the study centre on Day 7 for a Follow-up assessment. The following assessments will be performed (refer to Table 5 for further details):

- Abbreviated physical examination (including weight)
- 12-lead ECG
- Vital signs (including supine blood pressure, pulse rate and body temperature)
- Routine laboratory evaluations (biochemistry; haematology; coagulation; urinalysis; pregnancy test for females)
- eGFR assessment using the MDRD formula
- AE and concomitant medication recording

Subjects who are withdrawn from the study should, where possible, complete the procedures scheduled for the Follow-up assessment as soon as possible after withdrawal.

5.2.4 Unscheduled visits

An unscheduled visit is defined as any visit to the study centre outside of the Protocol specified time points due to safety reasons or when a repeated measurement is required (e.g., obvious measurement errors, measuring device failure, confirmation of out-of-range results), where the subject is seen by study personnel.

6 STUDY PROCEDURES

Procedures will be performed according to the Time and events schedule (Table 5).

The time point for PK blood collection will take priority over any other scheduled study assessments. Where scheduled study assessments are planned for the same time, the following sequence should be followed: (1) ECG recording; (2) vital signs assessments; (3) physical examination; (4) blood sampling, with PK blood sampling occurring within the windows presented below; and (5) meal (if applicable).

The time windows for PK sampling during the study are as follows:

- pre-dose: -60 to -30 minutes
- [REDACTED]: ±5 minutes
- [REDACTED] +3 minutes from end of infusion
- [REDACTED]: ±5 minutes
- [REDACTED]: ±15 minutes

All times relate to the infusion start time.

For safety assessments up to 2.5 hours post-dose, a time margin of ±15 minutes is allowed. For all other safety assessments, a time margin of 10% of the elapsed time since last medication dosing is allowed. Pre-dose assessments can be done between the time the subject wakes up and dosing. The order of pre-dose assessments may be adapted if necessary for practical reasons.

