3 STUDY DESIGN

3.1 Overall study design

This is a Phase I, open-label, single-dose study to evaluate the PK of MCI-186 in male and female subjects with severe hepatic impairment (Group 1, n = 6), defined using the Child-Pugh classification, and in male and female subjects with normal hepatic function (Group 2, n = 6). Subjects may be replaced or additional subjects may be enrolled to ensure a minimum threshold of 6 completing subjects per group.

- Group 1: Subjects with severe hepatic impairment (Child-Pugh total score of 10 to 14 [Grade C])
- Group 2: Healthy subjects with normal hepatic function to match Group 1 for age, body weight and gender

All subjects will be administered 30 mg MCI-186 over 60 minutes on the morning of Day 1. An infusion time window of ± 3 minutes is permitted.

Order of subject enrolment

Individual matching of healthy subjects will be performed for the subjects with hepatic impairment. Therefore, after the end of study assessments are completed in subjects with hepatic impairment, healthy subjects will be enrolled. Each healthy subject will be individually matched with a hepatic impairment subject with respect to age (± 15 years), body weight ($\pm 20\%$) and gender. Matched healthy subjects may be recruited by any study site, not necessarily by the same site which recruited the subject with hepatic impairment.

If there are significant safety concerns, the study may be stopped as described in Section 4.5.

Study periods and duration of study

The study consists of:

- A pre-admission Screening period (Day -21 to Day -2)
- A treatment hospitalisation period (Day -1 to Day 3) with single IV infusion of 30 mg MCI-186 over 60 minutes (including an infusion time window of ± 3 minutes) on Day 1, and PK blood sampling until 48 hours post-dose. All subjects will be confined to the study centre from Day -1 to Day 3. Safety assessments will be performed until discharge.
- A Follow-up Period (Day 7 +2 days). An end of study assessment will be performed.

The duration of participation for each individual subject is expected to be up to 30 days.

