7.1.1 Compliance

IMP will be administered by the Investigator or designee. The prescribed dosage, timing and mode of administration of IMP may not be changed. Any departures from the intended regimen must be recorded in the eCRF.

IMP accountability and subject compliance will be documented throughout the study period using study-specific IMP dispensing forms. The Investigator, or suitably qualified site personnel, will supervise/oversee the administration of IMP and the exact time of dosing will be recorded in the eCRF.

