#### 7.1.3.2. Pharmacokinetic Parameters

##### (1) Below the limit of quantification

For the calculation of PK parameters, actual sampling time (in hours rounded to 2 decimal places) relative to dosing should be used. Concentration below the limit of quantification (BLQ) will be imputed with a value of 0. For calculation of AUCs, missing data will be treated as if the respective sample never had been scheduled for the calculation by the linear-linear trapezoidal rule.

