#### (2) PK related

The allowable time window will be the following.

Pre-dose	Within 30 to 60 minutes before dosing
[REDACTED]	Scheduled time $\pm 5$ minutes
[REDACTED]	Within 3 minutes after dosing

[REDACTED]	Scheduled time ± 5 minutes
[REDACTED]	Scheduled time ± 15 minutes

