### **8.1.7. Study Drug Administration**

Study drug administration will be listed on the SAF (*Listing 16.2.5.2*).

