#### 8.4.2 Pharmacokinetic Parameters

The pharmacokinetic parameters listed in Section 2.2 will be calculated for each subject on active dose using non-compartmental model. All PK parameters will be listed (*Listing 16.2.6.4* and *Listing 16.2.6.5*).

The PK parameters will be summarized by each group (Groups 1 and 2). The following descriptive statistics will be calculated: N (number of subjects), n (number of valid observations), arithmetic mean, SD, CV%, minimum, median, maximum, geometric mean and geometric CV% (*Table 14.2.3.1* and *Table 14.2.3.2*).

For the descriptive statistics, the minimum and maximum will be presented according to following requirement:

- $t_{max}$ : will be presented with 2 decimal places.
- $C_{max}$ : will be presented with the number of significant digits they are reported with.
- Number of  $\lambda z$  points: will be presented with integer.
- Other PK parameters: will be presented with a fixed number of decimal places for each parameter. The number of decimal places is 2 decimal places corresponding to having 3 significant digits at the minimum by analyte.

Mean, SD, median and geometric mean will be presented with the number of decimals as follows.

- $C_{max}$ : will be presented with 4 significant digits.
- Other PK parameters: will be presented with 2 decimal places.

CV% and geometric CV% will be presented with 1 decimal place.

To visualize the relationship between measures of hepatic function and between the PK parameters of MCI-186 and the sulfate conjugate, the following scatter plots of  $AUC_{0-last}$ ,  $AUC_{0-\infty}$ ,  $AUC_{u0-\infty}$  and  $C_{max}$  (on the vertical axis) versus Child-Pugh score, Child-Pugh classification (Normal, Severe), albumin, bilirubin, prothrombin and eGFR (on the horizontal axis) with regression line, will be produced in linear scales:

The PK parameters of ( $AUC_{0-last}$ ,  $AUC_{0-\infty}$ ,  $AUC_{u0-\infty}$  and  $C_{max}$  of MCI-186 and the sulfate conjugate) vs (Child-Pugh score (*Figure 14.2.3.1.1* and *Figure 14.2.3.2.1*), Child-Pugh classification (*Figure 14.2.3.1.2* and *Figure 14.2.3.2.2*), albumin (*Figure 14.2.3.1.3* and *Figure*

14.2.3.2.3), bilirubin (Figure 14.2.3.1.4 and Figure 14.2.3.2.4), prothrombin time (Figure 14.2.3.1.5 and Figure 14.2.3.2.5) and eGFR (Figure 14.2.3.1.6 and Figure 14.2.3.2.6) plot will be produced for all subjects overlaid in one graph.

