## **Appendix 1      Pharmacokinetic Parameter Calculations**

- Actual blood sampling times will be used in the calculation of pharmacokinetic parameters
- All concentrations below the LLOQ will be set at zero for pharmacokinetic calculations
- When  $k_{el}$  is missing (or cannot be determined),  $t_{1/2}$ ,  $AUC_{0-\infty}$ ,  $AUC\%_{ex}$ ,  $CL/F$ ,  $MRT$ ,  $V_z/F$  and  $V_{ss}/F$  will not be calculated.

PK Parameter Calculations		
Parameters	Unit	Calculation
$C_{\max}$	ng/mL	will be determined by visual inspection
$AUC_{0-\infty}$	ng·h/mL	$AUC_{0-\infty} = AUC_{0-\text{last}} + C_{\text{last}} / k_{\text{el}}$ $C_{\text{last}}$ : last measurable concentration
$AUC\%_{\text{ex}}$	%	$AUC\%_{\text{ex}} = (AUC_{0-\infty} - AUC_{0-\text{last}}) / AUC_{0-\infty} \times 100$
$AUC_{0-\text{last}}$	ng·h/mL	will be calculated using the linear trapezoidal method and actual times $AUC_{0-\text{last}} = \sum_{i=1}^n \frac{t_i - t_{i+1}}{2} (C_{i-1} + C_i)$
$t_{\max}$	h	Measured time of $C_{\max}$
$t_{1/2}$	h	$t_{1/2}$ will be determined as: $t_{1/2} = \log_e (2) / k_{\text{el}}$

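### Does an end-of-infusion PK sample taken up to 3 minutes after the stop bias Cmax enough to need a new sampling window?

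*Protocol*

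**What the plan says.** - **Window.** Protocol Section 6 and SAP Table 1 (footnote 3) both give plus "3 minutes from end of infusion". SAP 7.2 gives "Within 3 minutes after dosing". Protocol Table 5, footnote 3, shows the same words after a ± sign, in the text as read from the PDF.
- **Infusion length.** Protocol 3.1 plans 60 minutes: "An infusion time window of ± 3 minutes is permitted". The stop may therefore fall at 57 to 63 minutes.
- **Cmax.** It is one of three primary endpoints. SAP Appendix 1 says that it "will be determined by visual inspection", with no correction for timing.
- **Times.** Protocol 6.6.1 has the actual time of every blood sample recorded. Protocol 7.1.1 says "the exact time of dosing will be recorded in the eCRF", together with any departure from the regimen. SAP 7.1.3.2 says "actual sampling time (in hours rounded to 2 decimal places) relative to dosing should be used".
- **Outputs.** SAP 8.4.2 lists tmax and summarises it by group; its minimum and maximum "will be presented with 2 decimal places". SAP 8.1.7 adds "Study drug administration will be listed on the SAF".
- **Comparison.** SAP 8.4.2 estimates the severe/normal ratio of geometric means with a 90% CI. Six subjects per group are planned.

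**The concern.** During a constant-rate infusion the concentration rises until the stop and then falls, quickly at first. Protocol Table 2 gives mean distribution half-lives of 0.27 h in adults and 0.17 h in elderly subjects. A window that opens at the stop therefore puts every permitted draw on the falling side. Using actual sampling times protects AUC, but it cannot restore a peak that was not sampled. Observed Cmax would tend to read low, by an amount set by how promptly staff draw.

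Two further points add to the unease. The sign in Protocol Table 5 differs from the other three places. The window is also counted from the stop, while Protocol 7.1.1 does not say in so many words that the stop time is recorded. If delays differed between groups, the Cmax ratio could be distorted.

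**Working it through.** The documents give no figure for this effect, so there is none to reproduce. I used a two-phase model and checked it against the protocol's simulated exposure.

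**Inputs.** Table 2 (0.5 mg/kg over 30 min): adults Cmax 888, AUC 742, half-lives 0.27 and 2.27 h; elderly 1041, 725, 0.17 and 1.84 h. Section 1.5 (30 mg over 60 min, simulated): Cmax 470, AUC 600.

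**Model.** With k = ln 2 / half-life and f the fast-phase share of AUC, the concentration at the stop of an infusion of length T is

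C(T) = (AUC/T) × [f(1 − e^(−k1·T)) + (1 − f)(1 − e^(−k2·T))],

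and each term then decays at its own rate.

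**Solving f, adults.** 888 / (742/0.5) = 0.598. The two build-up terms at 0.5 h are 0.723 and 0.142. So f = (0.598 − 0.142)/(0.723 − 0.142) = 0.786. The elderly set gives 0.782.

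**Anchor.** For 60 min and AUC 600, the adult set predicts 600 × (0.725 + 0.056) = 469, against the stated 470. The elderly set predicts 502.

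**Concentration relative to the peak, 60-minute infusion**

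| Draw | Adult set | Elderly set |
|---|---|---|
| 3 min before stop | 0.986 | 0.993 |
| 1 min after stop | 0.961 | 0.939 |
| 3 min after stop | 0.887 | 0.829 |

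Adult set at 1 minute: (0.725 × 0.958 + 0.056 × 0.995)/0.782 = 0.961. Solving f from 470/600 instead gives values within these ranges or very close to them. The shorter half-lives in Table 1 reach 7-8% at 1 minute only in extreme variants.

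**Average loss if draws are uniform over 0 to 3 min (assumed).** The log decline is nearly linear, so the mean is about half the 3-minute value: exp(½ ln 0.887) = 0.942 and exp(½ ln 0.829) = 0.910. Cmax reads 6-9% low. The log-SD from delay is |ln 0.887|/√12 = 0.035 to |ln 0.829|/√12 = 0.054.

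**Possible cap.** A ±5 min sample with a redacted nominal time is listed before this one. If it falls within the infusion, it limits the loss to 1-2% (5 min before the stop), 3-5% (10 min) or 5-9% (15 min). At 30 min before, it caps almost nothing.

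**Effect on the ratio**

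- *Same delay, same disposition:* both groups carry the same factor and it cancels exactly.
- *Same delay, clearance halved in the severe group (assumed, two-compartment form):* the fall at 1 minute is 2.3% instead of 3.9% (adult set) or 3.5% instead of 6.1% (elderly set). The adult ratio is inflated by 0.977/0.961 = 1.017; the elderly one by 1.027 from unrounded values. At 3 minutes: 0.934/0.887 = 1.053 and 0.898/0.829 = 1.083.
- *Random delays:* the SD of the log ratio is 0.035 to 0.054 × √(2/6), that is 0.020 to 0.031. The 90% CI factor is exp(1.8125 × log-SD × √(2/6)). With CV 171/888 = 19%, log-SD is 0.191 and the factor is 1.22; adding the delay variance gives 1.23. With CV 106/1041 = 10%, it goes from 1.11 to 1.12-1.13.

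**What a window of −3 to 0 minutes would do.** Draws would be at most 0.7-1.4% low in a 60-minute infusion. A draw timed for 57 minutes in a 63-minute infusion would be 1.3-2.6% low. If the infusion ended at 57 minutes and the draw came at 60, it would be 3 minutes late and the present loss would return. The permitted infusion length itself moves the true peak by about 4% either way, under any sampling window.

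**The ± sign.** Protocol Section 6, SAP Table 1 and SAP 7.2 agree on 0 to 3 minutes after the stop. The Table 5 footnote is visibly damaged: it sits beside redacted text and the pre-dose line has run into the next one. SAP Table 1 reprints the same schedule, from a SAP based on protocol v3.0, and has the plus sign.

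**The case for a change.** The strongest case for a change is that the loss falls on a primary endpoint, goes in one direction, and could be nearly removed without an extra sample. Cancellation in the ratio also depends on similar early disposition, and altered disposition is what the study is looking for. The groups are enrolled one after the other, possibly at different sites, so equal delays are not guaranteed. A systematic 1-minute difference would shift the ratio by 4-6%.

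The direction and arithmetic of the loss stand, and so does the condition on cancellation. Three things limit their weight. With reduced clearance and equal delays the distortion overstates the ratio, so it would not hide an increase in exposure. Nothing in the documents points to a systematic difference in delay. If one arose, sample times, the dosing listing and tmax by group would at least partly show it, since 3 minutes is 0.05 h and times are kept to 0.01 h.

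On the stop time, the point is thin. Neither the ±3 minute infusion limit nor the sampling window can be applied without knowing when the infusion ended, and the eCRF is not among the documents. A site would ordinarily record start and stop.

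**Conclusion.** No change to the plan follows. The window is stated consistently in three places, and a draw that starts at an observed stop is easier to follow than one that must anticipate it. Sampling just before the stop is a defensible alternative with its own failure mode, which makes this a fair operational trade-off. The odd sign in Table 5 is most likely a text-reading artefact; comparing it with the original is enough.

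The possible loss in absolute Cmax is 4-6% at 1 minute and 11-17% at 3 minutes. It rests on healthy-subject half-lives and on this sample setting Cmax, which redacted nominal times prevent anyone from confirming. For the ratio, equal delays leave nothing if disposition is alike, and about 1.7-2.7% (1 minute) or 5-8% (3 minutes) if clearance is halved. The documents give no disposition data for severe impairment, so that clearance value is only an assumption. With a 90% CI factor of about 1.11 to 1.22 at six per group, and AUC little affected, no change in the trial's conclusion is shown.
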